5.2 Follow-up Visits

Follow up visits will be performed daily from day 1 to day 28. One Brain imaging will be realized 24/48 hours after the aneurism treatment and one between day 28 and 45 after randomization. Transcranial doppler, MR CTA or DSA results will be collected when realized.

Day 1 to day 28

Vital status

Compliance to treatment

Experimental Treatment administration will be collected daily

Safety follow up

- Any major Cilostazol-related adverse event will be assessed:
 - Arrhythmia from auricular origin
 - Arrhythmia from ventricular origin
 - Abnormal bleeding
 - Allergy
- Other minor Cilostazol-related adverse events:
 - Tachycardia,
 - Fever
 - Fainting
 - Nausea
 - Vomiting
 - Stomach pain

Cerebral vasospasm

- Blood flow velocity increase on TCD
- Cerebral vasospasm diagnosed upon MR/CTA or DSA and its severity (mild/moderate/severe)

Delayed cerebral ischemia

- New focal deficit
- Glasgow point decrease
- No other cause

Treatment in the last 24 hours

- Continuous sedation
- Mechanical ventilation
- Extraventricular drain
- Therapy Intensity Level (TIP) for Raised ICP treatment (See Appendix 7)
- Hypertension therapy
- Vasopressors (epinephrine/norepinephrine/dobutamine)
- Milrinone administration
- Endovascular treatment (Balloon therapy or vasodilatator administration)
- Other treatment
- At ICU discharge, the modified Rankin scale will be evaluated by a blinded research technician in case of lost to follow up.

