Benchmark treatment	
Other procedures added by the research	
Standard of care of SAH patients is not modified by the study, may vary across centres but must include:
 
 - Enteral or IV nimodipine administration - Vasospasm / DCI monitoring and treatment

	
 - Radiological assessment of brain damage by cerebral TDM or MRI at day 10-21 
Face to face interview at 6 months by a clinical research assistant from the investigating centre or coordinating investigating centre.

Risks added by the research	1.1 Level C
Summary of the known and foreseeable benefits and risks for the research participants	
The incidence rate of SAH is high, 10 per 100.000 among which 85% are caused by a ruptured aneurysm: neurological deterioration is frequent during the ICU stay and is mainly due to delayed cerebral ischemia. The most recent meta-analysis showed that cilostazol significantly reduced poor outcome patients with SAH, with an Odds ratio of 0.52 [0.37 – 0.74] for unfavourable outcome (16). Our trial aims to confirm that a 14 days administration of 100 mg twice a day of cilostazol will reduce by 30% long-term disability and cognitive impairment of aneurysmal SAH. If so, our trial might dramatically change the therapeutic management of aneurysmal SAH, as nimodipine did long time ago. Collective benefit is also expected, including the reduction of the length of hospital stay and need for rehabilitation.
 
The study protocol will not interfere with other preventive or curative treatment of DCI and vasospasm, which will be kept to the discretion of the physician in charge.
 
Major secondary effects of cilostazol are arrhythmia, abnormal bleeding, and allergy (frequency not reported). Most frequent adverse reactions are headache (up to 34%), palpitation (up to 10%), and diarrhoea (up to 19%). These side effects are however reported in patients taking cilostazol as a long-term therapy. In previous trial on DCI prevention in SAH, 14 days administration of cilostazol appeared safe since no difference in major adverse events rate was observed between cilostazol and control groups.

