On angiograms in DSA or MR/CTA, the severity of vasospasm will be considered none or mild if there is a less 33% decrease in arterial diameter on angiography, moderate if there is a 34% to 66% decrease, or severe if there is at least a 67% decrease.

DSA or MR/CTA will be performed when:

- There are signs of delayed cerebral ischemia as described above.
- There is a severe impairment of cerebral blood flow velocity assessed with help of transcranial doppler (tCD), as defined below. tCD will be performed at the discretion of the physicians in charge. tCD is a non-invasive radiation free exam that can be used at bedside. Its repetition allows a better detection of vasospasm and is routinely performed. Cerebral vasospasm severity will be evaluated according to this scale:

Degree of cerebral blood velocity alteration	Mean flow velocity (cm/s)	Lindegaard ratio
Mild	120-149	3-6
Moderate	150-199	3-6
Severe	>200	>6

11. Occurrence of new cerebral infarcts

New cerebral infarct is considered when detected on the CT scan or MRI performed with 6 weeks, (or on the latest CT scan or MRI performed before death within 6 weeks, or at autopsy), but not present on the earlier CT or MRI scan performed between 24 and 48 h after early aneurysm occlusion and not ascribable to other causes such as surgical clipping or endovascular treatment. Hypodensities on CT imaging resulting from ventricular catheter or intraparenchymal hematoma should not be considered cerebral infarctions secondary to DCI.

12. Occurrence of cilostazol-related major adverse events, including: arrhythmia, abnormal bleeding and allergy.
13. Occurrence of cilostazol-related minor adverse events include: tachycardia, fever, fainting, nausea, vomiting and stomach pain.

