5.7 Distinction between care and research

TABLE: Distinction between procedures associated with "care" and procedures added because of the "research "

Procedures and treatments carried out as part of the research	Procedures and treatments associated with care	Procedures and treatments added because of the research
Treatments	DCI and vasospasm preventive and curative treatments (must include nimodipine administration)	Cilostazol or placebo administration during 14 days
Consultations	Routine visits from the physician in charge	Face to face interview at 6 months

Blood samples	Left to the discretion of the physician	None
Imaging, etc.	Imaging (CT scan, MRI, TCD) left to the discretion of the physician	All the imaging techniques evaluating secondary objectives are routinely realized

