9.3 Endpoint Adjudication Committee

- ✓ The adjudication committee's role is to analyze patient data in detail and conclude whether the event (endpoint) is present or not. The committee will therefore be made up of specialists in the pathology or endpoint of the trial. It is not necessarily independent of the trial, but the main thing is that it acts blindly. There is therefore a lot of preparatory work to provide the committee with anonymized and undated data.
 - Members of the committee: [name], [name], [name], [name]
 - Missions: Secondary endpoints adjudication
 - Operating methods: Meetings when 25, 50, 75 and 100% of the patients are monitored.
- ✓ Outcomes concerned :
Secondary endpoints adjudication
- ✓ Primacy of the opinion of the adjudication committee:
The adjudicated outcome takes precedence over that of the investigator

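### The later brain scan has three unreconciled timings, and the day 28-45 window runs past the 6-week limit of the new-infarct endpoint, whose start point is not stated

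*Protocol*

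**What the plan says.** **When the later scan is done**

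- Section 5.2: "One Brain imaging will be realized 24/48 hours after the aneurism treatment and one between day 28 and 45 after randomization".
- Synopsis, other procedures added by the research: standard of care must include "Radiological assessment of brain damage by cerebral TDM or MRI at day 10-21". No day 0 is defined.
- Section 5.7: under care, "Imaging (CT scan, MRI, TCD) left to the discretion of the physician"; under research, "All the imaging techniques evaluating secondary objectives are routinely realized". The research therefore adds no scan.
- Section 5.5: the chronology table goes from a day 0-28 column to the 6-month visit, with nothing for days 29-45.
- Section 8.1: radiological endpoints are collected daily during the ICU stay. No later collection is described there. Section 5.3 lists infarcts again at 6 months, but under a lead-in about events during the ICU stay.

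**What counts as an event**

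- Section 4.1.2, item 11: "New cerebral infarct is considered when detected on the CT scan or MRI performed with 6 weeks", or on the last scan before death in that period, or at autopsy, "but not present on the earlier CT or MRI scan performed between 24 and 48 h after early aneurysm occlusion". The synopsis and sections 3.2 and 5.3 give essentially the same definition. None says where the 6 weeks start.

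**Who decides**

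- Section 9.3: a committee adjudicates the secondary endpoints, and its conclusion prevails over the investigator's. The preparatory work is to "provide the committee with anonymized and undated data".

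**The concern.** The infarct definition depends on timing: absent on an early reference scan, present on a later scan inside a fixed limit. The protocol should therefore fix the later scan once, inside that limit. Instead a centre can follow the synopsis, section 5.2 or section 5.7 and image at quite different times. A centre that follows section 5.2 exactly can produce a scan that the endpoint definition does not accept.

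Two kinds of loss follow. If the only later scan is done late in the section 5.2 window, a real infarct may be visible but not countable. If the only later scan is done early in the synopsis window, an infarct that develops afterwards is not seen. Infarction is item 11 of 13 secondary criteria, and the synopsis groups it with the strong predictors of functional status. The hypothesis in section 2.1 is that cilostazol works by reducing delayed cerebral ischaemia (DCI), so uneven ascertainment weakens evidence on the proposed mechanism.

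**Working it through.** The plan gives no figure to reproduce; the check is a day count.

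**Inputs**

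- Endpoint limit: 6 weeks = 6 × 7 = 42 days (section 4.1.2); start not stated.
- Section 5.2 window: days 28 to 45 after randomisation, 45 − 28 + 1 = 18 days.
- Synopsis window: days 10 to 21; origin not stated.
- Longest lag from haemorrhage to randomisation: 96 h = 4 days (section 2.6). The synopsis counts inclusion from admission in one place but still requires treatment to start within 96 h of haemorrhage.
- Period in which DCI can occur: day 4 to day 21 after haemorrhage (section 10.3.3.1).

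**Step 1: do the two dated windows overlap?** Counted from the same origin, they do not; days 22-27 lie between them. If day 10-21 is counted from haemorrhage, it corresponds at the earliest to day 10 − 4 = 6 and at the latest to day 21 − 0 = 21 after randomisation. Occlusion precedes inclusion, so counting from occlusion falls between these cases. Under any of these origins the synopsis window ends before day 28, so no single scan satisfies both.

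**Step 2: which timing breaches 42 days?** Day 10-21 does not (21 < 42). Discretionary timing has no date, so it cannot breach the limit; it only fails to guarantee a scan. Day 28-45 does. With a lag of L days from the start of the 6 weeks to randomisation, the last eligible day after randomisation is 42 − L, and the number of window days outside is 45 − (42 − L) = 3 + L.

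| Lag L (days) | Last eligible day after randomisation | Window days outside | Share of 18 days |
|---|---|---|---|
| 0 (counted from randomisation) | 42 | 3 (43-45) | 17% |
| 1 | 41 | 4 | 22% |
| 2 | 40 | 5 | 28% |
| 3 | 39 | 6 | 33% |
| 4 (from haemorrhage, maximum lag) | 38 | 7 (39-45) | 39% |

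At L = 4 the latest scan allowed by section 5.2 is on day 45 + 4 = 49 after haemorrhage.

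**Step 3: the early window against the risk period.** Counted from haemorrhage, a scan on days 10-20 satisfies the synopsis but precedes the end of the DCI period at day 21. If it is the only later scan, subsequent infarcts are missed.

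**Step 4: can the windows be verified?** Two checks are needed: 24-48 h after occlusion for the reference scan, and 6 weeks for the later scan. Both need elapsed time. Section 9.3 promises undated material and does not say that elapsed days are supplied.

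**The case against.** The strongest reply is that these statements serve different purposes. The synopsis describes what standard of care must contain and does not name the infarct endpoint. Section 5.2 is the trial follow-up, and section 5.7 sorts procedures into care and research. A patient can have both a day 10-21 scan and a day 28-45 scan. This is fair, but the protocol never says that both are intended or which one serves the endpoint, and section 5.7 still leaves both to discretion.

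The second reply is that the definition accepts any scan within 6 weeks. An infarct seen on a day 10-21 scan, or on imaging done to exclude other causes of deterioration, counts even if the section 5.2 scan is late. This stands in full. An event is lost only if no earlier eligible scan showed it.

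The third reply concerns adjudication. A reader might infer that the committee cannot apply the definition at all. The document does not support that. Undated appears in a general description of blinded review and may mean only that calendar dates are removed. Section 5.1 collects the date of onset and the hours from symptoms to treatment, so elapsed days could be derived. What remains is a request to say so.

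A reader might also infer that all three timings conflict with the 6-week limit, or that 17% to 39% of infarcts or patients would be lost. Neither follows. Only the tail of the day 28-45 window passes the limit. The percentages count calendar days and would become shares of scans only if scans were spread evenly over the window, which is nowhere stated.

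**Conclusion.** The point holds as a consistency defect in the ascertainment of one secondary endpoint. The later scan has three unreconciled timings, the visit table and the collection text do not cover days 29-45, and a scan done exactly to section 5.2 can be ineligible. The excess is 3 of 18 window days if the 6 weeks start at randomisation and up to 7 of 18 if they start at haemorrhage. The upper figure assumes an origin that the protocol does not give and the maximum lag of 4 days.

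The number of events affected cannot be derived from the document, because neither the distribution of scan days nor the yield of earlier scans is given. Blinding and randomisation stratified by centre make a systematic difference between arms unlikely, so the expected harm is missed or unevenly detected infarcts and lost precision. The primary analysis of the 6-month mRS and the sample size do not use imaging and are unaffected. The change is worth making because a later analysis plan cannot recover scans taken at the wrong time.

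**What to change.** 1. State one window for the scan that serves the infarct endpoint, and use it in the synopsis and sections 5.2, 5.5, 5.7 and 8.1. If the day 10-21 assessment is a separate care scan, say so.
2. State the origin of the 6 weeks in section 4.1.2 and wherever the definition is repeated. The window must lie wholly inside the limit. If it is expressed in days after randomisation, it ends no later than day 42 if the origin is randomisation, and no later than day 38 (42 − 4) if the origin is haemorrhage.
3. Add the scan to the section 5.5 table, extend collection in section 8.1 beyond the ICU stay if the window can fall after discharge, and say in section 5.7 whether the scan is care or research.
4. In section 9.3 or the adjudication charter, state that calendar dates are removed but that days since haemorrhage and since occlusion are supplied for each scan.

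The cost is wording in the synopsis, about six sections and the charter, plus a field for the scan in the eCRF if none exists. No scan is added beyond what section 5.2 already schedules. If that scan proves not to be routine at every centre, declaring it a research procedure will have a budget and approval consequence.

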5.3 End of research visit at 6 months

The end of research visit will be made at 6 months or when the patient terminates the study.

Primary outcome

The physician, physical therapist, research assistant or research nurse will collect blindly the mRS if the patient is alive. A face-to-face structured interview will be held during which the modified Rankin scale will be assessed (Appendix 1, 17).

Functional and cognitive status will be collected during the patient's consultation at 6 months, with using:

- SAHOT Score
- MOCA score
- Return to work
- Activities of Daily Living
- Instrumental Activities of Daily Living

The in-hospital morbidity indicators will be collected, including:

- Length of Intensive Care Unit stay
- Length of hospital stay

The occurrence of cerebral vasospasm and DCI during ICU stay will be assessed, with collecting

-Delayed cerebral ischemia, defined as the occurrence of focal neurological deficit or a decrease of at least 2 points on the Glasgow Coma Scale, which does not occur immediately after aneurysm occlusion and which is not ascribable to other causes.

[figure not shown]
-Cerebral artery vasospasm, defined as a reduction of the diameter of the proximal cerebral artery on either CT-, MR- or catheter angiography

-Cerebral infarcts, considered when detected on the CT scan or MRI performed with 6 weeks, (or on the latest CT scan or MRI performed before death within 6 weeks, or at autopsy), but not present on the earlier CT or MRI scan performed between 24 and 48 h after early aneurysm occlusion and not ascribable to other causes

5.4 Expected length of participation and description of the chronology and duration of the research.

Inclusion period	42 months
The included subjects' length of participation, of which:	

 • Treatment period: • Follow-up period: 	2 weeks 6 months
Total research period:	49 months

5.5 Table or diagram summarising the chronology of the research

Actions	Inclusion visit	Day 0-28	End of research 6 months
Informed consent	x		
History	x		
Clinical exam*	x	x	x
Para-clinical exam*	x	x	x
Medical procedures (ECG, etc.)			
Dispensation of treatments		x	
Compliance	x	x	x
Adverse events		x	x

*A complete description of Clinical exam, paraclinical exam and tests are described specifically in each visit in section 5.1 to 5.3

5.6 End of the trial

The end of the research is defined as the date when the last visit of the last patient included in the study occurs.

5.7 Distinction between care and research

TABLE: Distinction between procedures associated with "care" and procedures added because of the "research "

Procedures and treatments carried out as part of the research	Procedures and treatments associated with care	Procedures and treatments added because of the research
Treatments	DCI and vasospasm preventive and curative treatments (must include nimodipine administration)	Cilostazol or placebo administration during 14 days
Consultations	Routine visits from the physician in charge	Face to face interview at 6 months

Blood samples	Left to the discretion of the physician	None
Imaging, etc.	Imaging (CT scan, MRI, TCD) left to the discretion of the physician	All the imaging techniques evaluating secondary objectives are routinely realized

5.8 Termination rules

5.8.1 Criteria and methods for prematurely terminating the research treatment

5.8.1.1 Different situations

- Temporary termination of treatment, the investigator must document the reason for stopping and restarting the treatment in the subject's source file and the case report form (CRF)
- Premature termination of treatment, but the subject is still included in the research, until the end of the subject's participation, the investigator must document the reason (if during the administration period, the patient get out of the ICU, the treatment will stop).
- Premature termination of treatment and end of participation in the research.

The investigator must:

- o Document the reason(s)
- o Collect the assessment criteria when participation in the research ends, if the subject agrees
- o In case of severe adverse event, subject will be closely monitored and followed.

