2.5 Identification and description of the experimental medication or medications

Cilostazol is a selective inhibitor of phosphodiesterase 3 (PDE 3) and antiplatelet agent. It is available in a tablet form and can be administered orally or through a gastric tube after being crushed.

"CASH" protocol, version 2.1 of 04/04/2025

2.6 Description and justification of the dosage, administration method, administration design and treatment period.

Patients will be included within the first 96 hours after SAH onset and randomly assigned to either cilostazol or placebo group. The dose of cilostazol will be 100mg twice a day for 14 days,.

The dosage of cilostazol is similar to the one tested in the four previous trial that documented benefit¹²⁻¹⁵.

Pharmacokinetics justification

We reviewed ten human studies that have directly quantified cilostazol's pharmacokinetics under varied dosing and design protocols. In healthy volunteers—primarily Korean subjects—one study reported an AUC of $12,100 \pm 4,880 \text{ ng}\cdot\text{h}/\text{ml}$, while Cmax values ranged from 283.7 to 1,623.9 mg/ml over doses from 25 to 300 mg. Elimination half-life consistently approximated 11 hours, and Tmax varied between 2.4 and 4 hours; one report estimated apparent clearance (CL/F) at 12.8 l/h.¹⁷⁻²⁶

Genetic analyses indicate that CYP3A5 and CYP2C19 variants significantly affect clearance and half-life, whereas ABCB1 appears to have no effect, overall the variance explained by polymorphism was 7% underlining a relevant but limited effect of genetics on cilostazol pharmacokinetics. A study in subjects aged 50 and older found no significant influence of age or gender. Investigations of drug interactions reveal no notable pharmacokinetic change when cilostazol is co-administered with probucol, but co-administration with simvastatin increases simvastatin AUC by 64% and its active metabolite by 31%. The drug will be delivered in oral form if patient is able to swallow the tablet. If not, tablets will be crushed by the nurse in charge of the patient, and given by oral or enteral route through feeding tube if required. Administration of crushed tablet will be standardized at specific timing in each center. In case a patient can eat a meal, the delay between administration and meal will be of 30 minutes minimum

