3 OBJECTIVES

3.1 Primary objective

Our main objective is to show that 100mg twice a day of cilostazol over 14 days improves the modified Rankin scale at 6-months in aneurysmal SAH treated with nimodipine, against placebo (Appendix 1)

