7 TREATMENT ADMINISTERED TO RESEARCH PARTICIPANTS

7.1 Description of the experimental medication or medications

7.1.1 Experimental medication 1

Cilostazol 100mg tablets

Packaging type : blisters

Two times a day (every 12 hours) for 14 days, 28 tablets in total

Storage: room temperature

Shelf life: 3 years

Oral form if patient is able to swallow the tablet. If not, tablets will be crushed by the nurse in charge of the patient, and given by oral or enteral route through feeding tube if required. Of note administration of crushed tablet will be standardized at specific timing in each center. In case a patient can eat a meal, the delay between administration and meal will be of 30 minutes minimum

Of note a market authorization (Autorisation de Mise sur le Marché) is available in France for cilostazol in chronic arteritis but no marketed anymore since 2010 in France. The GHU Paris Psychiatry and Neurosciences pharmacy will import cilostazol which is also marketed in Europe. The blinding as well as the creation of a placebo will be subcontracted to a competent GMP establishment. The logistic will be centralized by the pharmacy of the GHU Paris and the pharmaceutical circuit will be co-constructed between GHU Paris and pharmacies of the different investigator centres (storage and delivery).

7.2 Description of the non-experimental treatment or treatments (medications required for carrying out the research)

7.2.1 Non-experimental medication 1

As recommended by French and European guidelines, a preventive medication of DCI by nimodipine has to be administered during the ICU stay. The posology, route (IV or enteral) and length of treatment is left to the discretion of the caring physician.

7.3 Description of the traceability elements that accompany the experimental medication or medications

Designated pharmacists responsible for the receipt, handling and dispensing of study drugs (active and placebo) will maintain study drug records during the study: details of how all phases of dispensing and withdrawal of unadministered drugs will be monitored and controlled, and the patient code/kit code correspondence will be described in the Pharmacy Manual to be established prior to the start of the study.

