12 STATISTICAL ASPECTS

12.1 Description of statistical methods to be used including the timetable for the planned interim analyses

CASH is a multicentre, double-blinded, randomised, placebo-controlled, parallel-group superiority trial in adult, using an adaptive group-sequential design, to demonstrate that cilostazol plus nimodipine is safe and superior to nimodipine alone will improve modified Ranking Score (mRS) at six months.

Two interim analyses for futility and efficacy are planned.

Populations

For the statistical analysis, the following populations are defined:

Population	Description
Intent-To-Treat (ITT) Population	The ITT population will include all randomised participants. ITT participants will be analysed according to the randomised treatment, regardless of the actual treatment received. All efficacy analyses will be performed on the ITT population.
Per Protocol (PP) Population	The PP population will include all participants in the ITT with at least 80% of doses received to define adherence to treatment. The PP population will be used for supportive analyses of efficacy measures.
Safety Population (SP)	The SP will include all randomised participants who received at least one treatment (active or placebo). The SP will be analysed according to the actual treatment received. This population will be used for safety analyses.

Description of the statistical methods, including the timing of planned interim analyses

The statistical analysis plan (SAP) will be developed and finalised before the database is locked.

Below is a description of the planned statistical analysis. Further details will be presented in the statistical analysis plan (SAP).

All statistical analyses will be performed with SPSS version 26 or RStudio. For analyses performed with RStudio, the script used will be provided.

The baseline is defined as the last evaluation performed before the start of the study treatment, day 1 (V1).

All data collected after the start of the study treatment are defined as post-baseline.

Baseline characteristics will be summarised by the treatment group. The mean and standard deviation (SD) or median and interquartile range (IQR) for skewed variables will be summarised for continuous measures.

The proportion in each category will describe categorical variables.

In addition, the 95% confidence interval (CI) will also be calculated as indicated.

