12.2 Definition of Estimands in the CASH Trial

We define two primary estimands corresponding to the intention-to-treat (ITT) and per-protocol (PP) analyses, as well as an additional estimand incorporating neurological mortality.

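### Study drug must stop at ICU discharge, yet the regimen is stated as an unconditional 14 days and the per-protocol rule excludes some patients who were dosed exactly as required

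*Protocol*

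**What the plan says.** The stop rule appears once, in protocol section 5.8.1.1: "if during the administration period, the patient get out of the ICU, the treatment will stop". It sits in the bullet that begins "Premature termination of treatment, but the subject is still included in the research", so the patient stays in follow-up.

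The regimen is stated elsewhere without the ICU condition:
- Section 2.6: "The dose of cilostazol will be 100mg twice a day for 14 days".
- Section 3.1, primary objective: "100mg twice a day of cilostazol over 14 days improves the modified Rankin scale at 6-months".
- Section 5.7, care/research table: "Cilostazol or placebo administration during 14 days".
- Section 7.1: "Two times a day (every 12 hours) for 14 days, 28 tablets in total".

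The populations table in section 12.1 defines the per-protocol set by "at least 80% of doses received to define adherence to treatment" and gives it a supportive role. Section 12.2.2 ties the 80% to the doses prescribed over the 14-day period. The same section also says that the estimand concerns patients who finished the course with no break, and that only completers are analysed. The table in section 12.3 excludes early discontinuation from per-protocol and gives assessment of adherence as the reason.

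The status of this analysis varies. Section 12.2 opens with "We define two primary estimands corresponding to the intention-to-treat (ITT) and per-protocol (PP) analyses", while 12.2.2 is headed as a secondary estimand. For intention-to-treat, section 12.2.1 keeps patients who stop early in their randomised group (treatment policy).

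**The concern.** Leaving the ICU is a normal step in care. Section 5 plans a day-28 visit for patients already discharged from the ICU. Section 10.3.3.1 describes transfer to the ward once the remaining risk of neurological complications is judged low. A stop triggered by that step is part of the treatment under test, and the regimen and the analysis sets should describe it in the same way.

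They do not, with three consequences:
- **Conduct.** A pharmacist or ward reading section 7.1 would dose to day 14. One reading section 5.8.1.1 would stop at ICU discharge.
- **Primary result.** The comparison is of a course that may be shortened by ICU discharge, while the objective names the full 14 days.
- **Per-protocol result.** A set meant to reflect adherence removes patients for a stop that the protocol itself orders. Two analysts could also build different sets from the same section.

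**Working it through.** **Inputs.** 28 doses, one every 12 hours (section 7.1); 80% threshold (12.1 and 12.2.2); treatment start within 96 hours of the bleed (synopsis); stop at ICU discharge (5.8.1.1); delayed cerebral ischaemia possible from day 4 to day 21, with a peak around day 10 (10.3.3.1).

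**1. Threshold in doses.** 0.80 × 28 = 22.4, so at least 23 doses are needed. At two a day this is 23 / 2 = 11.5 days of dosing.

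**2. A fully compliant patient on either side of it.** No missed dose, stopped at ICU discharge:
- after 11 full days: 22 / 28 = 78.6%, excluded
- after 12 full days: 24 / 28 = 85.7%, meets the 80% rule

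Both patients were treated exactly as section 5.8.1.1 requires.

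**3. When dose 23 falls.** From dose 1 to dose 23 there are 22 intervals: 22 × 12 h = 264 h = 11.0 days. With the first dose at the 96-hour limit, dose 23 falls at 96 + 264 = 360 h, day 15.0 after the bleed. With an earlier start it falls sooner, but always later than day 11.0. Day 11.0 itself cannot be reached, because the patient must already be in the ICU with the aneurysm secured. To qualify, a patient must therefore still be in the ICU after the day-10 peak.

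**4. Worked example (hypothetical discharge date).** First dose at 96 h, ICU discharge on day 14: (14 × 24 − 96) / 12 = 20 doses, or 21 if one is given at both ends. That is 20 / 28 = 71% or 21 / 28 = 75%, so the patient is excluded.

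**5. Where section 12.2.2 disagrees with itself.** Discharge after 23 to 27 doses gives 23 / 28 = 82.1% to 27 / 28 = 96.4%. The 80% rule includes these patients. The completers-only rule, and the exclusion of early discontinuation in 12.3, leave them out.

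**6. Intention-to-treat.** Section 5.8.1.1 classes the stop as premature termination, and 12.2.1 handles that by treatment policy. All randomised patients stay in their arm and the comparison is valid. What it estimates is the assigned strategy as delivered: up to 14 days or until ICU discharge.

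**What cannot be computed.** The protocol gives no ICU length of stay, so the number of patients in steps 2 and 5 is unknown.

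**The case against.** The best defence is that the event is already covered. A planned course plus a section listing when dosing ends early is a common structure. Section 5.8.1.1 calls the stop premature termination, and the estimand sections have rules for that: keep in intention-to-treat, exclude from per-protocol. Section 12.2.2 states that it targets completers, so leaving out short courses is what it sets out to do. The 80% figure, the only numeric rule, can be read as the working definition of completion.

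Part of this stands. Intention-to-treat is handled, and an analysis of full-course patients is a legitimate choice. It does not rescue the adherence label: 12.1 and 12.3 present the set as a measure of adherence, and a patient stopped by the protocol has adhered. Nor does it reconcile the two inclusion rules. One could also read prescribed doses as doses due until the mandated stop, but 12.2.2 ties them to the 14-day period and 12.3 excludes early discontinuation without exception.

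Two stronger readings are tempting, and the protocol supports neither:
- A reader might infer that the trial is underpowered because early discharge dilutes the effect. That needs the share leaving early and the effect lost by a shorter course. The protocol gives neither.
- A reader might infer that the per-protocol estimate is biased in a known direction, because low-risk patients leave the ICU first. That selection concerns prognosis. How it changes the difference between arms cannot be derived from the text.

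**Conclusion.** The point holds as an inconsistency in the regimen and in a supportive analysis. The stop rule contradicts the unconditional 14-day course in sections 2.6, 3.1, 5.7 and 7.1. The adherence rule excludes fully compliant patients who leave the ICU before dose 23, and section 12.2.2 is contradictory for discharges after doses 23 to 27. These findings rest on the text and on 28 doses as the denominator.

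The consequence is limited. The primary comparison, its alpha and the sample size do not change; only the description of what is being estimated does. Despite the opening of section 12.2, the per-protocol analysis is best taken as supportive, as 12.1 and the heading of 12.2.2 have it. The share of patients affected and the direction of any per-protocol bias remain undetermined. The matter is worth settling in an amendment because sites and analysts cannot resolve it from the current wording.

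**What to change.** If the ICU stop is kept:
- State the regimen as up to 14 days or until ICU discharge in sections 2.6, 3.1, 5.7 and 7.1, with the synopsis to match.
- Use one per-protocol rule in 12.1, 12.2.2 and 12.3: at least 80% of the doses due until the earliest of day 14, ICU discharge or death. Other stops still count as non-adherence. Remove the completers-only wording, and call the analysis supportive throughout.
- Keep the set with at least 80% of 28 doses as a labelled full-course analysis.
- Report doses received and ICU-discharge stops by arm.

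Death belongs in the rule so that early deaths stay in and are counted as 12.2.2 intends. If early discharges were restored but early deaths dropped out, a 65% control rate would become 0.65 / (1 − d). That is 68.4% if d, the share dying early, were 5%, and 72.2% if it were 10%. Both values of d are assumptions.

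**Cost.** No new data are needed: daily administration (5.2) and length of ICU stay (5.3) are already collected. The wording touches the primary objective, so if it is a substantial modification it needs ethics committee and ANSM approval under section 14.9.

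**Downside.** The doses-due set depends on ICU stay, which is a post-randomisation variable and itself a secondary endpoint. It also counts very short courses as adherent. It must stay supportive and be read beside the full-course analysis.

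**Alternative.** Drop the stop rule and continue dosing on the ward to day 14. That matches the stated objective but requires ward dispensing and administration.
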